5. INVESTIGATIONAL AGENT/DEVICE/PROCEDURE INFORMATION

5.1 Investigational Agent/Device/Procedure

Blossom Smart Expander Technology is a FDA-approved (510K) medical device. It consists of a syringe assist device connected to the Mentor SPECTRUM® Adjustable Saline Breast Implant. Blossom Smart Expander Technology aims to achieve the same aforementioned reconstructive goals of traditional breast tissue expander implants while obviating the frequent percutaneous injections by means of automated slow and continuous saline injection based on pressure and volume measurements in the associated expander implant (Mentor SPECTRUM®). The Mentor Spectrum device is a onetime use device that is placed during surgery, but it is designed to allow providers to adjust volume (add or take out fluid from the prosthesis) after surgery in an outpatient setting through the remote port. In this study the Mentor Spectrum will be used in exactly the same way except rather than implant the remote port, the fill tube will be exteriorized at for a few centimeters to connect it to the Blossom controller device. The Mentor Spectrum will be treated like other tissue expanders in that at the conclusion of the expansion process the fill tube will be removed and ultimately the Spectrum will be removed and replaced with a permanent implant. The Mentor Spectrum can be used as a permanent implant in patients who desire a saline implant after removal of the infusion tube.

The Blossom Syringe Assist Device is intended to be used to assist the clinician in the delivery of sterile saline to fill temporary, removable tissue expanders. This device includes a battery powered controller to provide a regulated method for delivery of a specific volume of saline at a specific rate. Supplied with the controller in a kit are the following components: single use sterile 10cc luer lock piston syringe, transfer set with proximal connection to the controller, and saline reservoir including distal connections to the inflation port of the expander. The controller (pump) is 6.5" long, 3.5" tall, 1.25" wide and weighs 0.7lbs. AA batteries are changed every 3 days. There is a low battery indicator to remind patients to change the AA batteries every 3 days. The fluid path is clear, allowing for visual inspection of the content. If the device fails and a manual process is used. The device can be detached from the fill tube. The fill tube of the Mentor Spectrum device is externalized much like a drain and connected to the Blossom Syringe Assisted Device. It is expected to have the similar rate of infection as a standard drain.

A Mentor Spectrum® adjustable saline breast implant for expansion, coupled with the Blossom Syringe Assist device, will be inserted beneath the pectoralis major muscle in the usual fashion immediately after mastectomy. The nature of the surgery remains identical to that employed for conventional breast tissue expander insertion following mastectomy.

Please see attached instruction brochure for further information on Blossom Technology.

5.2 Availability

Marz Medical

5.4 Agent Accountability

The Blossom devices/kits will be stored together with the appropriate ordered breast implants for each individual patient.

6. **DOSE MODIFICATIONS**

No treatment modifications are envisioned.

If the investigational device were to fail to achieve the projected expansion of the breast skin, conversion to the traditional breast expander device with manual percutanous saline injections would be carried out, as indicated.

7. ADVERSE EVENTS AND REPORTING PROCEDURES

7.1 Potential Adverse Events

Since the Blossom Syringe device will be connected to and used with the Mentor SPECTRUM® Adjustable Saline Breast Implant the Risks include those common to all breast tissue expander implants procedures: capsular contracture, infection, extrusion, malposition, and pain. Importantly, these risks are due to the breast expander itself and as such are unavoidable in patients undergoing conventional 2-staged IBR. Furthermore, in the event of any pain due to volume fill, the Blossom technology device can easily be disconnected by the patient in a reliable and safe manner.

7.2 Adverse Event Reporting

Adverse events will be graded according to CTCAE v4.03. Both Serious and Non-Serious Adverse Events will be clearly noted in source documentation and listed on study specific Case Report Forms (CRFs). The Protocol Director (PD) or designee will assess each Adverse Event (AE) to determine whether it is unexpected according to the Informed Consent, Protocol Document, or Investigator's Brochure, and related to the investigation. All Serious Adverse Events (SAEs) will be tracked until resolution, or until 30 after the last dose of the study treatment.

SAEs CTCAE Grade 3 and above, and all subsequent follow-up reports will be reported to the Stanford Cancer Institute Data and Safety Monitoring Committee (DSMC) using the study specific CRF regardless of the event's relatedness to the investigation. Following review by the

DSMC, events meeting the IRB definition of 'Unanticipated Problem' will be reported to the IRB using eProtocol within 10 working days of DSMC review, or within 5 working days for deaths or life-threatening experiences.

8. CORRELATIVE/SPECIAL STUDIES

N/A

9. STUDY CALENDAR

	Pre- Study	Wk 1	Wk 2	Wk 3	Wk 4	Wk 5	Wk 6	Wk 7	Wk 8	Wk 9	Wk 10	Wk 11	Wk 12	Off Study
Blossom Syringe Assist Device, postoperative assessments ^a		X	X	X	X	X	X	X	X	X	X	X	X	
Informed consent	X													
Demographics	X													
Medical history	X													
Concurrent meds	X													
Physical exam	X													
Vital signs	X													
Height	X													
Weight	X													
Adverse event evaluation ^a X							X							
B-HCG	X													

^aDevice postoperative assessment and adverse events (AEs) evaluation will be conducted on a weekly basis for 12 weeks, with assessments in clinic every other week and by phone the alternative every other week.

NOTE: Baseline exams and tests performed as indicated above. Once investigational device is inserted surgically, the patient will undergo follow-up as mentioned previously until the second stage expander to implant exchange procedure.

10. MEASUREMENTS

10.1 Primary outcome measure: time to full expansion

- 10.1.1 This outcome will be measured on all subjects.
- 10.1.2 Defined as number of days until desired expansion volume is achieved. This outcome is not assessing a safety issue.
- 10.1.3 Outcome will be measured by calculating the number of days from expander placement to achievement of desired expansion volume.
- 10.1.4 Measurement time points include date of expander placement and date that desired expansion volume is reached. Follow-up will be 12 months.
- 10.1.5 Response is not the primary outcome.

10.2 Secondary outcome meausure: patient satisfaction

- 10.2.1 This outcome will be measured on all subjects.
- 10.2.2 Defined as patient satisfaction with expansion process.
- 10.2.3 Outcome will be measured by non-validated surveys (Breast Q) administered to patients in clinic in order to assess satisfaction. Patients will be asked to rank satisfaction on the following scale: very satisfied, somewhat satisfied, neutral, somewhat dissatisfied, very dissatisfied.
- 10.2.4 Measurement time points will be at postoperative clinic visits, which will occur at weekly and intervals during the expansion process. Total follow-up will be approximately 12 months.
- 10.2.5 Response is not the primary outcome.

10.3 Secondary outcome measure: incidence of complications

- 10.3.1 This outcome will be measured on all subjects.
- 10.3.2 Defined as complications associated with tissue expansion process, including expander extrusion, wound breakdown, infection, and/or device malfunction.
- 10.3.3 Outcome will be measured by assessment of these patients at postoperative clinic visits for these complications.
- 10.3.4 Measurement time points will be at postoperative clinic visits, which will occur at weekly intervals during the expansion process. Follow-up will be approximately 12 months.

10.3.5 Response is not the primary outcome.

10.4 Secondary outcome meausure: pain with expansion

- 10.4.1 This outcome will be measured on all subjects.
- 10.4.2 Defined as self-reported pain associated with expansion process.
- 10.4.3 Outcome will be measured by non-validated surveys (Breast Q) administered to patients in clinic in order to assess pain. Patients will be asked to rank pain level on a scale of 0 to 10, with 0 being the least and 10 being the most.
- 10.4.4 Measurement time points will be at postoperative clinic visits, which will occur at weekly intervals during the expansion process. Follow-up will be approximately 12 months.
- 10.4.5 Response is not the primary outcome.

11. REGULATORY CONSIDERATIONS

11.1 Institutional Review of Protocol

The protocol, the proposed informed consent and all forms of participant information related to the study (e.g. advertisements used to recruit participants) will be reviewed and approved by the Stanford IRB and Stanford Cancer Institute Scientific Review Committee (SRC). Any changes made to the protocol will be submitted as a modification and will be approved by the IRB prior to implementation. The Protocol Director will disseminate the protocol amendment information to all participating investigators.

11.2 Data and Safety Monitoring Plan

The Stanford Cancer Institute Data and Safety Monitoring Committee (DSMC) will be the monitoring entity for this study. The DSMC will audit study-related activities to determine whether the study has been conducted in accordance with the protocol, local standard operating procedures, FDA regulations, and Good Clinical Practice (GCP). This may include review of the following types of documents participating in the study: regulatory binders, case report forms, eligibility checklists, and source documents. In addition, the DSMC will regularly review serious adverse events and protocol deviations associated with the research to ensure the protection of human subjects. Results of the DSMC audit will be communicated to the IRB and the appropriate regulatory authorities at the time of continuing review, or in an expedited fashion, as needed.

11.3 Data Management Plan

The Protocol Director, or his/her designee, will prepare and maintain adequate and accurate participant case histories with observations and data pertinent to the study. Study specific Case Report Forms (CRFs) will document treatment outcomes for data analysis. Case report forms

will be developed using the REDCap database system and will be maintained by Stanford Box account. CRFs will be kept in a locked office, only accessible to the research team.

12. STATISTICAL CONSIDERATIONS

12.1 Statistical Design

This study is a prospective clinical trial.

12.1.1 Randomization

N/A

12.2 Interim analyses

There are no planned interim analyses

12.3 Descriptive Statistics and Exploratory Data Analysis

Measures of central tendency and measures of spread will be performed for the primary outcome (time to full expansion, in days)

12.4 Primary Analysis

(10.1): Time to full expansion

12.4.1 Analysis Population

All participants will be included in this analysis. Primary analysis will be an intent-to-treat principle.

12.4.2. Analysis Plan

Student's t-test will be applied to compare the primary outcome to values commonly reported in the literature in conventional 2-staged IBR.

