12.5.1 Analysis Population

All participants will be included in these secondary analyses. Any missing data will be reported as

such in the results.

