12.6.3 Effect size justification

The most extensive study on rapid breast expansion post-mastectomy with expander implants emanates from Memorial Sloan-Kettering Cancer Center and includes 370 breast reconstructions in 314 patients. Mean time until last in-office expansion was reported as 6.6 weeks postoperatively³. Among the most highly-cited papers on conventional 2-staged implant-based breast reconstruction complications also comes from Memorial Sloan-Kettering Cancer Center and incorporates data on 1522 breast reconstructions in 1221 patients. This paper describes an overall complication rate of 5.6% for the stage 1 breast tissue expander insertion procedure and expansion process in nonradiated patients, which is identical to our study population characteristics. Confidence intervals not applicable to these 2 studies. These studies provide the ideal baseline to compare to as they include the same target population from a well-respected cancer center and high number of patients.

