12.7 Criteria for future studies

As a pilot study, the criteria for success that would justify a fully powered study include: time to expansion (primary outcome) faster than described for the conventional technique in the literature (p<.05) as well as an incidence of complications comparable to that reported for conventional techniques in the literature. Lastly, acceptability by patients (based on the aforementioned surveys) will be taken into account.

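### The primary t-test cannot include a patient who never reaches desired volume; no rule covers her, and testing only available day counts hides failed expansions from the p<.05 criterion

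*Combined protocol and SAP*

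**What the plan says.** Section 10.1.3 defines the primary outcome as the "number of days from expander placement to achievement of desired expansion volume", and 10.1.1 has it measured in every subject. On its time frame, 10.1.4 says "Follow-up will be 12 months". Section 12.4.1 says "All participants will be included in this analysis. Primary analysis will be an intent-to-treat principle". Section 12.4.2 says "Student's t-test will be applied to compare the primary outcome to values commonly reported in the literature in conventional 2-staged IBR". The comparator is in 12.6.3: "Mean time until last in-office expansion was reported as 6.6 weeks postoperatively". In 12.7, the first condition for a fully powered study is a time to expansion "faster than described for the conventional technique in the literature (p<.05" level).

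The protocol foresees patients who may not get a day count. Section 6 plans conversion to a traditional expander if the device does not achieve the projected expansion. Section 4.2 removes patients who withdraw consent. Section 4.1 lets the patient disconnect the device for pain. Section 10.3.2 lists as complications "expander extrusion, wound breakdown, infection, and/or device malfunction".

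The only sentence on missing data, "Any missing data will be reported as" such, is in 12.5.1. It belongs to the secondary analyses and concerns reporting, not analysis.

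**The concern.** A one-sample t-test needs a number for each patient. The endpoint exists only once desired volume is reached, so a patient who never gets there has no number, and the test and the intent-to-treat population cannot both be honoured. The easy way out is to test the day counts that exist. That removes the worst outcomes. Compared with any analysis that treats a failure as a long time, it shortens the trial mean, shrinks the SD and makes the device look faster.

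With ten patients, each is a tenth of the data, and the result feeds the first go criterion in 12.7. The study is open and single-arm (2.4), so a rule written after the outcomes are known could be shaped by them.

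**Working it through.** **Inputs from the documents.** n = 10 (12.6.1). Benchmark 6.6 weeks × 7 = 46.2 days (12.6.3). Expected expansion about 2-3 weeks, or 14-21 days (section 4). Weekly assessments for 12 weeks, or 84 days (section 9). Criterion p<.05 (12.7), taken as two-sided because the plan does not say. The sample size has no derivation, so there is no figure of the plan's own to reproduce.

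**Assumed inputs.** The documents give no SD, failure rate or failure time. Two completer scenarios are used: mean 18 days, SD 4 (within the protocol's expectation), and mean 28 days, SD 8 (slower than it expects). A failure is either dropped or, for illustration, scored at 84 days.

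**Failures dropped.** With m completers, t = (mean − 46.2)/(SD/√m) on m − 1 df. For three failures in ten, m = 7:
- 18/4: t = −28.2/(4/√7) = −18.65, p = 0.000002.
- 28/8: t = −18.2/(8/√7) = −6.02, p = 0.0009.

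Only the degrees of freedom and the standard error change, so a 30% failure rate barely registers.

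**Failures scored at 84 days.** With k failures and m = 10 − k, the mean is (m × mean + 84k)/10 and the variance is [(m − 1)SD² + (mk/10)(84 − mean)²]/9.
- 18/4, one failure: mean 24.6; variance (128 + 3920.4)/9, SD 21.21; t = −21.6/6.71 = −3.22.
- 18/4, two failures: mean 31.2; variance (112 + 6969.6)/9, SD 28.05; t = −15.0/8.87 = −1.69.
- 28/8, one failure: mean 33.6; variance (512 + 2822.4)/9, SD 19.25; t = −12.6/6.09 = −2.07.
- 28/8, two failures: mean 39.2; variance (448 + 5017.6)/9, SD 24.64; t = −7.0/7.79 = −0.90.

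| Completers | Failures of 10 | p if dropped | p if scored at 84 days |
|---|---|---|---|
| 18, SD 4 | 1 | <0.0000001 | 0.010 |
| 18, SD 4 | 2 | 0.0000002 | 0.125 |
| 28, SD 8 | 1 | 0.0001 | 0.068 |
| 28, SD 8 | 2 | 0.0004 | 0.39 |

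**How likely is a failure?** The chance of at least one in ten is 1 − (1 − q)^10: 18%, 40% or 65% at an assumed q of 2%, 5% or 10%.

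**Loss unrelated to expansion.** In 200,000 simulated trials with lognormal times and true mean 46.2, random loss of 0, 1 or 2 of ten gave a false faster result in 4.9/5.0/5.0% (CV 0.3) or 7.0/7.1/7.2% (CV 0.5). The excess over the nominal 2.5% comes from the assumed skewness. Random loss adds essentially nothing, so the problem is confined to patients missing because expansion failed or was not tolerated.

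**The case against.** The failure route that section 6 describes is conversion with manual filling. A converted patient can still reach desired volume, and she then has a day count under 10.1.3. This stands: she is not part of the gap, although the plan does not say whether her day counts. Her late finish need not reverse the result either: at 18/4, one finisher at day 60 or 70 gives p=0.0004 or 0.002, and two give 0.007 or 0.032.

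The scored values are illustrations, since no document proposes 84 days. This also stands. At the protocol's expected 2-3 weeks, one failure scored at 84 days does not overturn significance.

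The documents do not say how the 6.6-week series handled its own failed expansions. If that figure is a completers' mean, ranking only this trial's failures as slowest makes the comparison uneven against the device. A reader might infer that dropping failures biases the comparison with the benchmark by a known amount. The documents do not support that: the trial's own mean falls, but the size of any bias against 46.2 days is unknown.

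Failures may also show up elsewhere. Section 12.7 asks for comparable complications and considers acceptability, and 4.2 stops the study for excess complications or a clearly more ineffective device. This protection is partial. None of these has a numeric limit, and 10.3.2 names neither under-expansion without a complication nor disconnection for pain.

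**Conclusion.** The concern holds for patients who never reach desired volume for reasons tied to the expansion. For them the stated test does not fit the stated endpoint and population, and no section fills the gap. On available day counts, even three failures in ten leave p at 0.000002 or 0.0009 under the assumed inputs. Under an 84-day score, significance is lost with two failures at 18/4 or one at 28/8. These sizes depend on assumed means, SDs and scores. The direction depends only on a failure being treated as longer than the completers' mean.

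A reader might infer that the plan intends to exclude failures. It does not say so: it is silent, and exclusion is merely what a t-test on available values does. Nor do the documents show that failures will occur. The point should be fixed before outcomes are known, because a p<.05 go criterion rests on it.

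**What to change.** In 12.4, analyse days to desired volume as time-to-event in all enrolled patients, with a Kaplan-Meier or cumulative-incidence curve and the median with its CI set against 46.2 days. State that:
- patients who never reach volume because of explant, device failure without later completion, or withdrawal related to expansion (including pain) are kept as not expanded through the 12-month follow-up;
- withdrawals unrelated to expansion, with the reason recorded, are censored at last contact;
- by intent-to-treat, a converted patient's actual day to volume counts in the primary analysis, and a sensitivity analysis treats her as not expanded on the device.

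Beside the primary result, report how many of ten reached volume on the device with an exact 95% CI (8/10: 44% to 97%). Give the completers-only t-test as a sensitivity analysis. Say that the benchmark's handling of failures is unknown. Reconcile 4.2, 4.3, 5.1 and 6, which do not agree on whether a converted patient stays in the study and has her date collected: 4.3 allows conventional expansion only on withdrawal, while section 6 converts as indicated and 5.1 mentions a manual process.

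Section 12.7 should then name the result that its p<.05 uses. An exact two-sided sign test against 46.2 days is one option, with failures counted as not faster. Nine of ten faster gives 2 × 11/1024 = 0.021, and eight of ten gives 2 × 56/1024 = 0.109, so two failures in ten cannot reach p<.05 however fast the others are. At a true mean of 28 days (lognormal, CV 0.3/0.5) with no failures, its power is 96%/75% against 99.7%/89% for the t-test. It also sets a median against a published mean: under a lognormal null with mean 46.2 its false faster rate is 2.6%/4.2%, against a nominal 2.5%.

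The cost is a paragraph of text, a reconciling sentence and some power, with no new patients or visits.

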12.5 Secondary Analysis

(10.2): patient satisfaction

(10.3): incidence of complications

(10.4): pain with expansion

12.5.1 Analysis Population

All participants will be included in these secondary analyses. Any missing data will be reported as

such in the results.

12.5.2 Analysis Plan

Survey data for secondary outcomes 10.2 and 10.4, as described in previous sections, will be tabulated. Secondary outcome 10.3 will be analyzed with Student's t-test in order to compare with complication rates reported in the literature for conventional 2-staged IBR.

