3.1 Inclusion Criteria

3.1.1 Diagnosis of breast cancer or reason for prophylactic mastectomy (e.g., BRCA mutation and/or strong family history of breast cancer), both unilateral or bilateral mastectomy.

- 3.1.2 No prior breast surgery (excluding biopsy and lumpectomy) or breast radiation.
- 3.1.3 Women age 18 years or older, no race-ethnic restrictions.
- 3.1.4 Ability to understand and the willingness to sign a written informed consent document.
- 3.1.5 No life expectancy restrictions.
- 3.1.6 ECOG or Karnofsky Performance Status will not be employed.
- 3.1.7 No requirements for organ and marrow function.

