4.2 Criteria for Removal from Study

Patients will be removed from the study in the event of withdrawal of consent. Patients would then be eligible for placement of conventional tissue expanders. The study as a whole would only be terminated prematurely if the Blossom device proved to be clearly more ineffective, since traditional tissue expansion is still a safe and effective method of expansion. The study will terminate if there is increased incidence of complications noted above rates of complications reported in the standard tissue expander-implant reconstruction.

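### Section 12.5.2 assigns an unspecified Student's t-test to a complication proportion in ten patients, so whether an excess over 5.6% is flagged depends on which form is run

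*Combined protocol and SAP*

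**What the plan says.** Section 12.5.2 of the combined protocol and SAP sets the method: "Secondary outcome 10.3 will be analyzed with Student's t-test in order to compare with complication rates reported in the literature". It does not say whether the test is one-sample or two-sample, one-sided or two-sided, or at what level.

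Section 10.3 defines the outcome as "complications associated with tissue expansion process, including expander extrusion, wound breakdown, infection, and/or device malfunction". Section 12.6.1 plans ten patients, section 2.4 describes a single group, and section 12.5.1 includes all participants in the secondary analyses.

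The benchmark is in section 12.6.3: an "overall complication rate of 5.6% for the stage 1 breast tissue expander insertion procedure", from a paper that "incorporates data on 1522 breast reconstructions in 1221 patients". The section does not say whether 5.6% is a rate per patient or per breast. Section 3.1 admits "both unilateral or bilateral mastectomy".

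Section 12.7 gives the criteria for moving to a fully powered study: time to expansion "faster than described for the conventional technique in the literature (p<.05) as well as an incidence of complications comparable" to that in the literature. The 5% level is attached to time to expansion only, and the complications criterion has no margin or threshold. Separately, section 4.2 says: "The study will terminate if there is increased incidence of complications noted above rates of complications reported" for standard reconstruction. It names no test or threshold either.

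**The concern.** A t-test relies on a sample mean that is roughly normal and a usable estimate of its standard error. With ten zeros and ones and an expected rate near 5.6%, neither holds. The standard deviation is fixed by the count itself: it is zero when there are no events, and it grows as events accumulate, which blunts the test just when an excess appears.

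The complication rate is one of the criteria for a larger trial, and 12.5.2 is the only planned comparison that informs it. Because the form of the test is open, two analysts following the same sentence could reach opposite conclusions from the same count.

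**Working it through.** The plan states no power, critical count or calculated sample size for this comparison, so there is no figure of its own to reproduce.

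**Inputs.** n = 10 (12.6.1); benchmark p0 = 0.056 (12.6.3); reference series of 1221 patients or 1522 reconstructions (12.6.3). Assumed, because the plan does not say: the patient is the unit, 5.6% is a per-patient rate, and the level is 5%.

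**One-sample t-test.** With k events, the mean is k/10, SD = sqrt[(k/10)(1 − k/10)(10/9)], t = (k/10 − 0.056)/(SD/sqrt 10), on 9 df. At k = 3: SD = sqrt(0.21 × 10/9) = 0.483, SE = 0.153, t = 0.244/0.153 = 1.60. At k = 4: SD = 0.516, SE = 0.163, t = 0.344/0.163 = 2.11.

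**Exact binomial.** P(X ≥ k) with X ~ Bin(10, 0.056). P(0) = 0.944^10 = 0.562; P(1) = 10 × 0.056 × 0.944^9 = 0.333; P(2) = 45 × 0.056² × 0.944^8 = 0.089. Hence P(X ≥ 2) = 0.105 and P(X ≥ 3) = 0.016.

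| Events of 10 | t | t, two-sided p | t, one-sided p | Exact one-sided p | Clopper-Pearson 95% CI |
|---|---|---|---|---|---|
| 0 | SD = 0 | – | – | 1.00 | 0% to 30.8% |
| 1 | 0.44 | 0.670 | 0.335 | 0.438 | 0.3% to 44.5% |
| 2 | 1.08 | 0.308 | 0.154 | 0.105 | 2.5% to 55.6% |
| 3 | 1.60 | 0.145 | 0.072 | 0.016 | 6.7% to 65.2% |
| 4 | 2.11 | 0.064 | 0.032 | 0.0016 | 12.2% to 73.8% |
| 5 | 2.66 | 0.026 | 0.013 | 0.0001 | – |

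The one-sample t-test first flags an excess at 5/10 if two-sided and at 4/10 if one-sided. The exact test does so at 3/10, with a true type I error of 0.016. If the true rate were 30%, the chance of flagging it is P(X ≥ 5) = 15%, P(X ≥ 4) = 35% and P(X ≥ 3) = 62% respectively.

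**Pooled two-sample t-test.** Take the reference as 85/1522 (5.6% rounded to whole events) and the trial as 2/10. The difference is 0.200 − 0.0558 = 0.144. The pooled variance is (9 × 0.1778 + 1521 × 0.0528)/1530 = 0.0535, almost entirely that of the reference series. SE = sqrt[0.0535 × (1/10 + 1/1522)] = 0.0734, t = 1.96, two-sided p = 0.0497. Other roundings and denominators give 0.0498 (68/1221), 0.0520 (86/1522) and 0.0526 (69/1221). The number of nonradiated patients behind the 5.6% is not given, so the p-value can be placed only at about 0.05. Welch's unequal-variance form behaves like the one-sample test (3/10 p = 0.145; 4/10 p = 0.064).

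**Sensitivity to the unit.** If 5.6% is per breast, the per-patient benchmark depends on the share of bilateral cases. It stays at 5.6% with none. With all ten bilateral it reaches 1 − 0.944² = 10.9% (breasts independent) or 2 × 5.6% = 11.2% (never both affected). Across 5.6% to 11.2%, the exact p at 3/10 runs from 0.016 to 0.092, so the 3/10 contrast depends on the unit. At 4/10 the exact p runs from 0.0016 to 0.019, against 0.064 to 0.112 for the two-sided one-sample t-test, so that contrast holds throughout.

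**The case against.** The strongest reply is that the plan never says one-sample, so missing 3/10 is a property of one reading. That is fair. A reader might infer that the plan as written is insensitive to an excess of complications. The documents do not support this: the pooled two-sample reading is too sensitive instead, and the 4/10 miss disappears if the one-sample test is one-sided. What stands is that every form is unsuitable and that the forms disagree.

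A reader might also infer that a non-significant result at 3/10 or 4/10 would count as comparable and release the next trial. Section 12.7 does not link that word to a p-value. Section 4.2, read plainly, might be engaged by such a count whatever the t-test shows, but it is as undefined as 12.7, so it weakens the consequence without removing it.

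Nor does 0/10 leave the trial with nothing to say. The count can still be reported beside 5.6%; only the planned test fails.

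Finally, this is a secondary outcome in a ten-patient pilot with no power claim, and no test does well at that size. That is true: the exact test flags a true 20% rate only 32% of the time. It argues for resting the criterion on an interval, not for keeping the t-test.

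**Conclusion.** Wrong as written, and worth fixing, at the modest weight that suits a secondary outcome in a pilot. Section 12.5.2 names a method that does not fit a proportion in ten patients and leaves its form open. On the assumptions listed, the smallest count flagged is about 2, 4 or 5 of 10 depending on the t-test chosen (pooled two-sample, one-sample one-sided, one-sample two-sided), against 3 of 10 for the exact test. In the most likely single outcome at a true 5.6%, no events, the one-sample t-test cannot be validly computed.

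The choice of an unsuitable test follows from the documents alone, given a per-patient count, which section 10.3 implies but does not state. The particular counts rest also on the 5% level and on 5.6% being a per-patient rate. At n = 10, non-significance under any test could not establish comparability.

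**What to change.** In 12.5.2, replace the t-test for outcome 10.3 with:

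> *The number of patients with at least one complication will be reported out of all enrolled patients with a two-sided Clopper-Pearson 95% CI and set against the literature rate expressed per patient. Any test will be an exact one-sample binomial test, one-sided at the 2.5% level, to agree with the CI. Device malfunction will also be reported separately.*

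The 2.5% level matters. A one-sided 5% test would contradict the 95% interval at 3/10 for any benchmark between 6.7% and 8.7%; at 8%, for example, p = 0.040 although the lower limit is 6.7%. The patient should be the only unit, because two breasts in one patient are not independent and both exact methods need independent units.

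In 12.6.3, state whether 5.6% is per patient or per breast and, if per breast, restate the benchmark per patient.

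In 12.7, state that a lower 95% limit above the benchmark will be reported as an excess (first reached at 3/10, lower limit 6.7%, if the benchmark is 5.6% per patient). Any lower count will be reported as not shown to differ, not as comparable, because even 0/10 has an upper limit of 1 − 0.025^(1/10) = 30.8%.

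Sections 4.2 and 12.7 both set complications against published rates without defining the comparison, and their wording must be reconciled. How the study should stop is for the investigators to decide.

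The cost is a few sentences and one check of the cited paper, with no new data or patients. The downside is a more modest safety statement, from an exact test that is itself weak at this sample size.
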